### 2. Abstract:

The present study investigates the effects of an exercise intervention on neurological correlates of aging with sedentary older adults. Whereas chronological age measures the number of days a person has been alive, biological age refers to an individual's immediate state of health in relation to the average individual across age groups. As progressive biological aging in sedentary adults is associated with declines in the neurological motor system, an important application of aging-related research is the identification of treatment interventions that may slow, stop or even reverse the biological aging process.

Aerobic exercise may exert such anti-aging effects on the neurological system, particularly in relation to patterns of interhemispheric communication. Recent studies by the principal investigator have indicated that aerobic activity level might maintain upper extremity motor performance. This study extends the previous cross-sectional research using a direct exercise intervention to measure effects on upper extremity function and patterns of motor activity within the brain.

The current study proposes to use modern neuroimaging (functional magnetic resonance imaging [fMRI] and diffusion tensor imaging [DTI]) and neurophysiological (transcranial magnetic stimulation [TMS]) techniques to investigate the effects of aerobic exercise on aging related changes of the neurological system. We will recruit 40 older, sedentary individuals. Our previous research has indicated that aging is associated with a loss of interhemispheric inhibition present in TMS (duration of the ipsilateral silent period) and during the performance of unimanual tasks in fMRI. We hypothesize that, initially, the sedentary adults will show patterns of motor activity in TMS and fMRI consistent with that of older adults, whereas after training, brain activity will be more reflective of patterns typically seen in younger adults.

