*Functional Imaging and Neurophysiological Analyses.* Functional images will be analyzed and overlaid onto structural images with the Analysis of Functional Neuroimaging (AFNI) program (Cox, 1996). To minimize the effects of head motion, time series images will be spatially registered in 3-dimensional space. The average functional intensity of each acquired slice for every subject will be normalized to the mean intensity of all slices for all subjects to control for differences in functional intensity between subjects. A subject's data will be excluded from further analyses if any time series of a subject is judged from visual inspection to contain a significant number of images with gross artifacts or residual motion.

*fMRI Analysis.* The current study is concerned with the response of the ipsilateral primary motor cortex during actions performed by right hand. It is hypothesized that sedentary aged adults will initially show an increase in metabolic activity (i.e. – a positive BOLD response) in this area. To assess this, an analysis of average hemodynamic (impulse) response functions in the right primary motor cortex will be performed. These impulse response profiles will be tested across session using repeated measures ANOVA. Significant differences will be assessed at the individual

subject and group level.

For group analysis of intervention effects, anatomic and functional images will be interpolated to volumes with 1 mm^3 voxels, co-registered, and converted to stereotaxic space of Talairach and Tournoux (1988) using AFNI. Estimates of hemodynamic response functions (HRFs) generated from a deconvolution procedure will be spatially smoothed using a 5 mm full-width half-maximum (FWHM) Gaussian filter to compensate for variability in structural and functional anatomy across participants. Area under the curve (AUC) of the HRF's will be entered into a voxel-wise two-way mixed-design ANOVA (age grouping as the between subjects factor, session as the within-subjects factor). Additional pair-wise comparisons of age groupings will be performed using Student's t-test ( $p < .05$ , False Discovery Rate corrected) on a voxel-by-voxel basis with left and right primary motor cortices selected as regions of interest (ROI). Pairwise comparisons will be computed for all motor response conditions.

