## 7. Statistical Analysis

**Statistical Analysis for Specific Aim 1.** We will model each of the outcome measures in Aim 1 (upper extremity) jointly using a mixed linear model to determine whether the mean responses of the groups are significantly different across the time points. We expect that modeling the outcomes jointly, using subject as a random factor, will allow for some gains in power. Our fixed factors will be time, treatment group and their interaction. This model will enable us to estimate the overall effects of time and treatment, and most importantly, how the effects of treatment differ with time.

**Statistical Analysis for Specific Aim 2.** For each of the outcome measures in Aim 2 (changes in fMRI and TMS activity during unimanual tasks) we will use a mixed linear model to determine whether the mean responses of the groups are significantly different across the time points. Our fixed factors will be time, treatment group and their interaction. This model will enable us to estimate the overall effects of time and treatment, and most importantly, how the effects of treatment differ with time.

**Statistical Analysis for Specific Aim 3.** For each of the outcome measures in Aim 3 we will use a mixed linear model to determine whether the mean responses of the groups are significantly different across the time points. Our fixed factors will be time, treatment group and their interaction. This model will enable us to estimate the overall effects of time and treatment, and most importantly, how the effects of treatment differ with time. Level of interhemispheric inhibition will be characterized by proportion of ipsilateral motor cortex recruited during fMRI tasks, ipsilateral silent period in TMS, and level of diminution of MEP size in the interhemispheric inhibition protocol in paired-pulse TMS.

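### The hypothesis of a positive right-M1 response at entry is given only a session-wise ANOVA, which cannot test it, and the plan does not say whether that ANOVA or the Section 7 mixed model governs right-M1 BOLD

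*Combined protocol and SAP*

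**What the plan says.** Under Specific Aim 2, the fMRI Analysis paragraph states the hypothesis that "sedentary aged adults will initially show an increase in metabolic activity", which it explains as a positive BOLD response in the ipsilateral motor area. To assess this it says that "an analysis of average hemodynamic (impulse) response functions in the right primary motor cortex will be performed", and then: "These impulse response profiles will be tested across session using repeated measures ANOVA". It adds that differences will be examined at individual and group level, without naming a reference value. The Abstract carries a related expectation: "initially, the sedentary adults will show patterns of motor activity in TMS and fMRI consistent with that of older adults".

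Two other fMRI analyses are named. The next paragraph of the same section, on intervention effects, gives a voxel-wise mixed ANOVA with "age grouping as the between subjects factor, session as the within-subjects factor", followed by pairwise t-tests of age groupings "with left and right primary motor cortices selected as regions of interest (ROI"). Section 7, for each Aim 2 outcome including fMRI, gives a mixed linear model: "Our fixed factors will be time, treatment group and their interaction". It singles out the change in treatment effect over time as the most important result.

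**The concern.** The hypothesis concerns a level at one time: is the right-M1 response above zero at the first assessment? The ANOVA concerns change: do the session means differ? Neither answer implies the other. The trial's rationale is that sedentary older adults begin with positive ipsilateral activation that training may lower, so following the text as written leaves a stated premise untested.

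The second problem is one of precedence. Read alone, the session ANOVA cannot distinguish a difference between trainings from a shift common to both groups, such as practice on or habituation to a repeated scanner task. The Section 7 model can make that distinction for the comparison between groups. Specific Aim 1's Research Design lists changes in fMRI among the primary outcomes, yet nothing says which analysis a statement about right-M1 BOLD should rest on. The two could point in opposite directions.

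**Working it through.** **What each named analysis can answer for right M1**

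| Analysis | Factors named | Entry level against zero? | Difference between trainings? |
|---|---|---|---|
| Region-average ANOVA (Aim 2, fMRI Analysis) | session | no | no |
| Voxel-wise ANOVA and t-tests (same section) | age grouping, session | no | no; Section 6 enrols a single 60 to 89 population and defines no age groups |
| Mixed model (Section 7, Aim 2) | time, treatment group, interaction | no such contrast named | yes |

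The third column has no yes in any row, and the fourth has one. So the entry test is missing, while the between-training test exists in Section 7 but is not reconciled with Section 5.

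**The plan's own figure.** Section 7 gives one design figure for these outcomes: an effect size of 0.83 with 20 per group, assuming a two-sample t-test on post-minus-pre differences. At alpha 0.05 that corresponds to power of 72.5% two-sided or 82.5% one-sided (noncentral t). Power and sidedness are not stated, so 0.83 can be neither confirmed nor called wrong. The present point does not rest on it. It is used below only as a between-group difference in row C.

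**Illustration.** From the plan: N = 40, 20 per group. Assumed, because the plan gives none: SD 1, within-person correlation ρ = 0.5, one summary value per session, and the mean patterns shown. Simulated rates come from 10,000 trials per row.

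- Entry test: one-sample t on 39 df, two-sided 0.05, counting positive results. Noncentrality = mean × √40 = 0.5 × 6.325 = 3.16, giving 86.9%.
- Session ANOVA with S sessions: F on S−1 and 39(S−1) df, noncentrality λ = 40 × Σ(μⱼ − μ̄)² / (1 − ρ).
- Row A: all means equal, so λ = 0 and the rate is the nominal 5%.
- Row B: means 0, 0, −0.5, −0.5; Σ = 4 × 0.25² = 0.25; λ = 40 × 0.25 / 0.5 = 20, giving 97.1%.
- Row D: means 0.5, 0.5, 0; Σ = 1/36 + 1/36 + 4/36 = 1/6; λ = 40 × (1/6) / 0.5 = 13.3, giving 90.4%.
- Row C, interaction: deviations of ±0.415 at the third session; λ = 40 × 0.415² × (2/3) / 0.5 = 9.19, on 2 and 76 df, giving 76.2%.

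| Row | Truth | Session ANOVA | Group × session | Entry above zero |
|---|---|---|---|---|
| A | entry +0.5, no change (4 sessions) | 5.0% | 5.3% | 86.7% |
| B | entry 0, both groups fall 0.5 | 96.9% | 5.5% | 2.5% |
| B2 | entry −0.5, both groups rise 0.5 | 97.1% | 5.1% | 0.0% |
| C | entry +0.5, opposite changes of 0.415 (3 sessions) | 3.4% | 76.4% | 86.8% |
| D | entry +0.5, both groups fall 0.5 (3 sessions) | 90.7% | 5.1% | 87.1% |

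The simulated rates agree with the formulas. Rows A, B and B2 show that the session ANOVA carries no information about the entry level. Rows C and D show that it and the group-by-session term can give opposite answers.

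**Sensitivity to the assumptions.** With five sessions, a linear drift shared by both groups and ρ from 0.3 to 0.7, λ = 40 × 0.05625 / (1 − ρ) for a total drift of 0.3 SD, and 40 × 0.15625 / (1 − ρ) for 0.5 SD. The session ANOVA then rejects in about 25% to 56% and 64% to 97% of trials, respectively. The size depends heavily on the assumed values; the direction does not.

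**The case against.** A reader might infer that the session ANOVA is the only test planned for right-M1 fMRI, and so that no comparison of the trainings exists. The documents do not support that. Section 7 specifies time, treatment group and their interaction for the Aim 2 fMRI outcomes, and the voxel-wise analysis also takes right M1 as a region of interest. The between-training half of the point is therefore a conflict between sections, not an omission.

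It can also be said that the response functions are estimated from rest and active blocks, so the sign at entry will be visible; that the ANOVA may never have been meant as a test of sign; and that positive entry activation is not itself a specific aim. The first and last of these are true, and the second is possible. They reduce the stakes, but the hypothesis is still stated and no test of it is named. Nor would a test against zero settle the broader Abstract expectation, which covers TMS as well and refers to an older-adult pattern.

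The strongest objection is to over-correcting. It would be tempting to let the omnibus group-by-session term decide every training claim and to treat session change as purely descriptive. Both groups receive both trainings, and groups are split again after the second intervention. If each training shifts the response equally and persistently, that term rejects at about 5%. If only aerobic training works, by a persistent 0.5 SD, it rejects in about 23% to 50% over five sessions (λ = 2 / (1 − ρ), ρ 0.3 to 0.7, assumed). The 3-month stretching wait, assessed before and after, is a within-person control that such a rule would discard. This objection stands, and the fix respects it.

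**Conclusion.** The point holds in two parts. First, the test attached to the entry hypothesis does not test it, and no section supplies one. This follows from the text and needs no numerical assumption. Second, the session ANOVA alone cannot support a difference between trainings; Section 7 has a model that can, but the plan does not say which governs right-M1 BOLD. Section 7 also leaves open which fMRI summary enters the Aim 2 model: response profile, area under the curve (AUC), or the proportion of ipsilateral motor cortex recruited that is named under Aim 3.

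The simulated rates rest on assumed SD, correlation and patterns of change. They should not be read as this trial's error rates, and nothing in the documents shows that a drift across scans will occur. Nor do the documents say that either result may be reported as the fMRI finding, so an inflated false-positive rate from choosing between them is not established.

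**What to change.** In the fMRI Analysis paragraph, test the entry hypothesis with a one-sample contrast of the right-M1 AUC at assessment 1 against zero, two-sided 0.05, for one of the two motor tasks named in advance. State that the session ANOVA is not used for that hypothesis.

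Reconcile that paragraph with Section 7 by stating that between-training claims on right-M1 AUC come from the Section 7 mixed model, and that a session-only effect is not evidence of a difference between trainings. Name the sessions the model covers, since groups are split again after the second intervention. Within-person change during training may still be reported, for example against the change over the waiting period; that comparison assumes any repeat-scan shift is similar in the two intervals.

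The cost is wording and one extra contrast. No additional scans or participants are needed.

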### **Specific Aim 3) To determine if role of exercise duration in maintaining or enhancing motor performance and levels of interhemispheric inhibition.**

*Introduction:* Behavioral interventions (motor strength and coordination) have been shown to be effective in improving upper extremity motor performance in older adults (Christou, 2011; Engler et al., 2011), however the duration of these gains appear to be short-lived (Toraman, 2004; Ivey et al., 2000). After as little as a few weeks of detraining, motor strength and coordination in the upper extremity rapidly begins to return to pre-intervention levels (Carvalho et al., 2009; Toraman, 2005; Toraman & Ayceman, 2005;). Evidence from exercise interventions assessing gait and locomotion have shown that exercise programs over a longer term (>6 months) are associated with improved proprioception, fewer falls and better balance (Arnold et al., 2008). However, the comparison of outcomes of upper extremity function in elderly adults respective of exercise duration remains largely unexplored. In addition to comparing the effects of short-term exercise (3 months) versus behavioral training (3 months) on upper extremity function, the current proposal will evaluate if a longer-term (6 months) exercise program

can maintain or enhance upper extremity function and associated levels of interhemispheric inhibition. Further, we will inquire as to how the long-term exercise program has affected the general quality of life in our sample.

**Research Design:** As shown in the figure below, the study groups will be split after the second intervention. Participants will then be either enrolled in 26 week exercise program or placed in no treatment group with no physical activity requirements other than a light stretching regimen. Participants will be given elastic Therabands during the waiting phase and asked to engage in light stretching exercises of the large muscle groups of the arms, trunk and legs (prescribed in the Theraband training manual and instructed by research associates at first assessment). During this six-month period, participants enrolled in the exercise group will continue to adhere to the exercise regimen described in detail above (participants will be provided with an exercise bike for home use). Participants in the no aerobic exercise intervention will be asked to engage in the Theraband stretching training similar to the waiting period protocol. At the end of the six months, all participants will return for a final/followup behavioral and neuroimaging assessment. At this time, participants in the no exercise intervention group will be given an exercise bicycle for home use as compensation.

### Measures for Specific Aim 3.

1. Cycle ergometer test VO2max assessment (described in detail below)
2. Upper extremity performance measures as listed in Specific Aim 1.
3. Imaging measures as listed in Specific Aim 2.
4. Daily Activity Log. All participants will track exercise activity over the course of each day while in the study until the final 12 week follow-up. At this time, they will receive a summary of their activity reports and physical fitness progress.
5. Physical Activity Readiness Questionnaire. The questionnaire, inquires about perceived difficulties in general physical activities involving voluntary exercise.
6. Quality of Life Survey: We will also administer the standardized SF-36v2 Health Survey questionnaire that assesses an individual's quality of life in comparison with previous points of remembrance.
7. Epworth Sleepiness Scale- self report used to determine the level of daytime sleepiness.

8. Pittsburgh Sleep Quality Index- 10 item questionnaire examining participants sleep habits over the past month.
9. Sleep Profiler: These monitors will provide pre and post-intervention objective data on sleep quality, patterns, and continuity that will supplement the Pittsburgh Sleep Quality Index, Epworth Sleepiness Scale. They are non-invasive wearable recorders with 3 EEG electrodes housed with a headband placed just below the hairline that provide study-validated information including total sleep time, REM sleep, sleep efficiency, snoring intensity and frequency, and arousal. Participants will be provided a brief orientation and instruction on how to properly wear the device. The device requires minimum setup, and the wearable headband is similar to a headband that might be worn at the gym. It is battery powered, with up to 16 hours of recording between charges, and data is stored and easily downloaded via USB from the device.

### **Additional measures for Specific Aim 3:**

**Fitness Assessments:** Initial fitness level will be assessed using three measurements. The initial assessment is the participant's self-report on the two phone-administered exercise inventories. Secondly, during the first participation session a direct test of the participant's aerobic fitness level is to be completed at the Atlanta VAMC aerobic fitness testing center. This test will also be used as an outcome measure for aerobic fitness for the duration of the study. The direct fitness assessment will consist of cycling ergometer assessment with trained research staff following ACSM (American College of Sports Medicine) testing guidelines (listed under Human Subjects Protection) and under the direction of an exercise physiologist, [name]. [name] will also assist with the training of participants on self-directed cycling and theraband exercise.

### **Possible Discomforts and Risks:**

#### Behavioral Testing:

Patients may experience some frustration if they have trouble with cognitive testing. Researchers will be trained on how to handle frustration by taking breaks, allowing patients to express frustration, and offering encouragement. As noted above, we will also include items that the participants can answer correctly to minimize frustration. In the vast majority of patients, these techniques are adequate to deal with frustrations.

#### Magnetic Resonance Imaging (MRI):

More than 150 million diagnostic magnetic resonance studies have been performed worldwide. The vast majority of these procedures were completed with no sign of patient injury (Schenck, 2000). There is a high degree of patient safety with an fMRI because of the miniscule value of magnetic susceptibility and lack of ferromagnetic

components of human tissue. Studies have ranged in magnetic field intensities from 1.5 to 8T. No negative cardiac, physiological, or cognitive effects were noted (Kangarlu & Robitaille, 2000). Therefore, long-term effects on human health from magnetic resonance imaging are unlikely. Those at risk for injury include those with indwelling ferromagnetic material (e.g. foreign object in eye, surgical implant) or an implanted bioengineering device (e.g. pacemaker, infusion pump), due to the possible interaction with a magnetic field. Subjects identified as at risk from the screening checklist will be excluded from the study.

Another potential hazardous effect is related to the high level of noise produced by the machinery during imaging. Unprotected, patients can experience hearing loss. For this reason, individuals will be given foam earplugs to wear to minimize this risk.

Additionally, some individuals are perceptible to experiencing distress during the fMRI process. The small, closed-in space may trigger anxiety. Participants will be screened for claustrophobia, generalized anxiety disorder, post-traumatic stress disorder, or obsessive-compulsive disorder.

Further, persons who are pregnant (or could be pregnant) or those with a seizure disorder should not undergo magnetic resonance imaging, and will be excluded.

Subjects may have early stages of disease, not previously diagnosed, detected through the use of MRI. A trained neurologist is available to the investigators to evaluate the findings and determine if there is pathology present or a normal variant should the investigators suspect that the imaging shows abnormalities. If pathology is present or suspected, subjects will be counseled about what the findings are and what should be the next steps for clarification of ambiguous findings or seeking help with pathological findings. This is not a risk in the conventional sense of physical harm or disease, but does pose a potential psychological risk to the patient.

#### Transcranial Magnetic Stimulation (TMS):

There may be some discomfort associated with application (skin preparation) and removal (tape removal) of the EMG surface sensors or reflective markers during TMS testing. Some slight irritation is possible, although measures are taken to reduce the likelihood of this occurrence, which in any case should disappear in a few days.

Subjects sometimes report low level, but easily tolerable scalp discomfort from TMS. Occasionally, subjects report headaches from TMS that are relieved by common over-the-counter pain medications. However, both of these issues are less of a problem in the particular scalp areas that we will be stimulating.

Possible effects on hearing have been described so participants will be asked to wear earplugs during TMS. As with any electronic device or appliance, using it the wrong way could result in electric shock. While this is very, very unlikely, it cannot be completely left out as a possibility. To mitigate risk, all participants will remove any metal objects on their person prior to TMS stimulation.

